    - cluster of differentiation 4 (CD4),
    - cluster of differentiation 8 (CD8),
    - plasma HIV RNA and
    - gestational age.
6. To assess potential interference of maternal antibodies with infant vaccine-serotype PNC anti-capsular antibody responses after the first 2 doses of PCV-10 and determine if interference of maternal antibodies differs in PCV-10 from PPV-23 and from placebo recipients.
  - Outcome measure: ELISA-measured IgG PNC antibody concentrations at weeks 16 and 24 in infants

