#### Infant Schedule:

Study visits for infants were conducted at birth (with a window of +7 days), week 8, which should be  $\leq 7$  days before the 1st dose of PCV-10 (with a window of +14 days), week 16, which should be  $\leq 7$  days before the 2nd dose of PCV-10 (with a window of  $\pm 28$  days), week 24, which

should be  $\geq$  28 days after the 2nd dose of PCV-10 (with a window of 28 days), or for Invasive Pneumococcal Disease (IPD).

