### Infants:

This is an as-treated analysis including only the infants born to women who have been vaccinated and those who have received the PCV-10 vaccination prior to the week 8 study visit.

Summaries will include the proportion (%) and 95% CI of infants born to mothers who received PCV-10 or PPV-23 vaccines who had ELISA-measured IgG PNC antibody levels  $\geq 0.35\mu\text{g/mL}$  at 8 weeks of age for  $\geq 1$  serotype listed above. The difference in proportions between the two groups will be assessed using a Chi-Square test.

In the case of twins, one child will be chosen at random for the primary immunogenicity analysis. Sensitivity analyses will repeat these summaries in the event that twins are enrolled in the study, re-doing the analysis using the other sibling.

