## 5.4 Secondary Objectives

Summaries will include:

- i) means (or medians if data are not normally distributed) and 95% CI of mean ratio of infant/mother ELISA-measured IgG PNC antibody levels across the serotypes listed above, measured at birth/delivery;
- ii) Summary table with proportion (%) and 95% CI of women in the each treatment group who had a  $\geq$ two-fold increase to each serotypes in ELISA-measured IgG PNC antibody concentrations from baseline to week 4 after immunization in Step 1;
- iii) Summary table with proportion (%) and 95% CI of women by treatment arm who had ELISA-measured IgG PNC antibody levels  $\geq 0.35\text{ug/mL}$  at week 4 after immunization in Step 1, at labor&delivery, and at week 24 post-delivery in Step 1 to  $\geq 1$  of the serotypes listed above;
- iv) Summary table with proportion (%) and 95% CI of women who had a two-fold increase to  $\geq 1$  serotype in ELISA-measured IgG PNC antibody concentrations from baseline to week 4 after immunization in Step 1 vs the women who achieved this from entry to Step 2 until week 4 post immunization in Step 2 (for each of the two vaccines). The analyses will exclude the women who delivered prior to week 4 in Step 1;
- v) Correlations between ELISA-measured IgG PNC antibody concentrations at weeks 4 in Step 1, in the women who received PPV-23 or PCV-10, and the following variables (measured at week 0): maternal age, ethnicity, cluster of differentiation 4 (CD4) count, cluster of differentiation 8 (CD8) count, plasma HIV RNA and gestational age;
- vi) Summary table with proportion (%) and 95% CI of infants born to mothers who received PCV-10 or PPV-23 vaccines who had ELISA-measured IgG PNC antibody levels  $\geq 0.35\text{ug/mL}$  at 16 and 24 weeks of age for  $\geq 1$  serotypes listed above;
- vii) Summary table with mean (95% CI) number of serotypes with levels  $\geq 0.35\text{ug/mL}$  at weeks 16 and 24 of age in study infants.

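### Section 5.4 items vi and vii cannot answer secondary objective 6: residual maternal IgG counts as infant response, and no comparison with placebo is set up

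*SAP*

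**What the plan says.** Secondary objective 6 (SAP 3.2) is "To assess potential interference of maternal antibodies with infant vaccine-serotype PNC anti-capsular antibody responses after the first 2 doses of PCV-10", and to "determine if interference of maternal antibodies differs in PCV-10 from PPV-23 and from placebo recipients". Its outcome measure is "ELISA-measured IgG PNC antibody concentrations at weeks 16 and 24 in infants".

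Section 5.4 gives two summaries that bear on it:

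- Item vi is a "Summary table with proportion (%) and 95% CI of infants born to mothers who received PCV-10 or PPV-23 vaccines who had" IgG of at least 0.35 ug/mL "at 16 and 24 weeks of age for" one or more serotypes.
- Item vii is a "Summary table with mean (95% CI) number of serotypes with levels" of at least 0.35 ug/mL at the same two visits, in study infants as a whole.

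The infant schedule in section 5.1 puts the week 8 visit at most 7 days before the first "dose of PCV-10 (with a window of +14 days), week 16, which should be" at most 7 days before the second dose. Week 24 is at least 28 days after the second dose.

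Section 5.3 applies the same 0.35 ug/mL criterion "at 8 weeks of age for" one or more serotypes as the primary infant measure. Section 4.2 limits that analysis to infants who have not yet had PCV-10.

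**The concern.** Before the first infant dose, the SAP reads IgG of 0.35 ug/mL or more as a comparison between infants of PCV-10 and PPV-23 mothers, so there it can only stand for antibody passed on by the mother. After the first dose, the same cut-off on the same assay becomes the evidence about the infant's own response. ELISA IgG does not show who made the antibody, and neither item uses the week 8 level. The suspected cause of interference (more maternal antibody) therefore raises the score that is meant to detect it.

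Three further features weaken the two items:

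- The objective names placebo recipients, but item vi leaves their infants out and item vii states no arm comparison.
- A criterion of at least one serotype out of eight is easily met by nearly everyone.
- The week 16 sample follows one dose only, while the objective concerns two.

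At stake is a conclusion of no interference that the data could not support.

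**Working it through.** The SAP gives no concentration, effect size or power for objective 6, so there is no figure of its own to reproduce.

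**Inputs from the SAP:** cut-off 0.35 ug/mL; 8 serotypes (3.2); week 8 before dose 1, week 16 before dose 2, week 24 after dose 2 (5.1). Nominal times from week 8 are t = 56 and 112 days.

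**Assumed, not in the SAP:** maternal IgG half-life h = 25, 35 or 45 days.

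**1. Carry-over with no infant response.** The residual fraction is 2^(−t/h). A serotype still passes if the week 8 level is at least 0.35 × 2^(t/h).

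| h (days) | Fraction left, wk 16 | Wk 8 level needed, wk 16 | Fraction left, wk 24 | Wk 8 level needed, wk 24 |
|---|---|---|---|---|
| 25 | 0.212 | 1.65 | 0.045 | 7.81 |
| 35 | 0.330 | 1.06 | 0.109 | 3.22 |
| 45 | 0.422 | 0.83 | 0.178 | 1.96 |

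The week 16 window is ±28 days. For a draw at week 12 (t = 28) the levels needed fall to 0.76, 0.61 and 0.54 ug/mL.

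**2. Effect on an item vii count if it were split by arm.** This is an illustration by simulation, with 200,000 draws per cell. Total IgG is residual maternal plus own IgG, and the count is 8 × P(total ≥ 0.35). Further assumptions: week 8 geometric mean 0.25 ug/mL in placebo infants and 0.6, 1.0 or 1.5 in infants of vaccinated mothers; own geometric mean 0.5 at week 16 and 1.5 at week 24; SD of log IgG 1.1. Interference is a proportional cut in own IgG in the vaccinated arms. The ranges cover 9 settings (3 half-lives × 3 levels) and show vaccinated minus placebo, in serotypes.

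| Interference | Wk 16 own IgG only | Wk 16 total IgG | Wk 24 own IgG only | Wk 24 total IgG |
|---|---|---|---|---|
| 0% | 0 | +0.69 to +1.47 | 0 | +0.09 to +0.35 |
| 20% | about −0.6 | +0.29 to +1.29 | about −0.3 | −0.17 to +0.26 |
| 30% | about −1.0 | +0.01 to +1.20 | about −0.5 | −0.37 to +0.21 |
| 50% | about −2.0 | −0.70 to +0.99 | about −1.2 | −0.96 to −0.02 |

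At week 24, of the 27 cells with interference, 18 keep a negative sign. The 9 positive ones are 6 at 20% and 3 at 30%, none above +0.26.

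**3. Ceiling of item vi.** If serotypes were independent, P(at least 1 of 8) = 1 − (1 − p)^8. For p = 0.3 this is 94.2%, and for p = 0.5 it is 99.6%. Positive correlation between serotypes would lower these figures.

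**4. What a pre-dose adjustment can show.** Let M be the week 8 level, f the residual fraction and R the infant's own IgG, so that total = Mf + R.

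- *Slope.* If R does not depend on M, the slope of log total on log M is Mf/(Mf + R), which is positive. With h = 35, M = 1.0 and the own means above, it is 0.330/0.830 = 0.40 at week 16 and 0.109/1.609 = 0.07 at week 24. Carry-over thus pushes the slope up, much less so at week 24.
- *Fold change.* Total/M = f + R/M falls as M rises, even without interference. At week 24 with h = 35 and R = 1.5, it is 0.109 + 6.0 = 6.1 for M = 0.25 but 0.109 + 1.5 = 1.6 for M = 1.0.

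**The case against.** The strongest defence is one of scope. These are descriptive summaries for a secondary objective with no test attached. The list in 5.4 need not be exhaustive, and table detail is left to an Analysis Implementation Plan that is not shown. The outcome measure in 3.2 is the concentration itself, so a fuller analysis is not ruled out. This softens the point but does not remove it: section 1 says the SAP focuses on the analyses that address the secondary objectives, and raw concentrations at weeks 16 and 24 would mix the two sources as well.

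Week 16 can also be read as a deliberate first look after dose 1, followed by week 24 after dose 2. On that reading the fault is one of labelling.

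A reader might infer three stronger things that the SAP does not support:

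- *That following 5.4 would show infants of vaccinated mothers doing as well as or better than placebo infants.* Item vi contains no placebo infants and item vii states no split. The plain defect is that the comparison is not set up.
- *That the direction of interference would be reversed in general.* Reversal is mainly a week 16 possibility, and every level and half-life behind it is assumed.
- *That the week 8 level is a primary outcome in every infant.* A week 8 visit is scheduled for infants generally, but the primary comparison names the two active-vaccine arms only.

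It is also fair to say that no simple adjustment is clean. The week 8 slope mixes carry-over with interference, and the week 8 level arises after randomisation and lies on the path from maternal arm to infant response.

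**Conclusion.** The point stands in this form: items vi and vii, followed as written, cannot answer objective 6. That much follows from the text alone: a total-IgG cut-off with no link to the pre-dose level, no placebo infants in item vi, no arm comparison in item vii, and a week 16 sample taken before dose 2.

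The size rests on assumptions. With a half-life of 25 to 45 days, carry-over alone passes the cut-off from week 8 levels of 0.83 to 1.65 ug/mL at week 16 and 2.0 to 7.8 ug/mL at week 24. Masking or reversal is plausible at week 16. At week 24 the effect is mostly attenuation, and in the illustration a 50% reduction never changed sign. These figures show what is possible, not what this trial's data will show.

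**What to change.** First, reconcile section 5.3 (infants who have received PCV-10 before week 8) with section 4.2 (infants who have not), so that week 8 is a true pre-dose value. Also confirm that week 8 assays exist for placebo-arm infants.

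Then, in 5.4:

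1. Make week 24 (at least 28 days after dose 2) the main time point for objective 6, and label week 16 as after dose 1.
2. By serotype and for all three arms, report geometric mean IgG with unadjusted arm contrasts, as the randomised comparison.
3. Beside these, regress log IgG on the infant's week 8 log IgG and maternal arm. State that carry-over biases the slope upward: a negative slope is conservative evidence of interference, while a null or positive slope does not exclude it. State also that week 8 is a post-randomisation variable.
4. Add a sensitivity analysis that subtracts expected residual maternal IgG over a stated half-life range, using actual sampling dates and a stated rule for results at or below zero.
5. Treat uncorrected fold change as supportive only, because a high pre-dose level lowers it without interference.
6. Keep items vi and vii as descriptive.

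The cost is SAP wording and one model per serotype, mainly on samples already scheduled. Infants without a valid week 8 sample drop out of the regression, and the decay correction rests on an assumed half-life.

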## 6 Report Components

Detailed descriptions of the content of each of the following sections are given in the AIP.

1. Accrual
2. Baseline characteristics
3. Study status
4. Protocol deviations
5. Data timeliness and completeness
6. Safety:
  - a. Primary safety outcomes
  - b. Deaths
  - c. Hospitalizations
  - d. Concomitant medications
7. Primary immunogenicity outcomes
8. Secondary outcomes

## 8 Timetable for primary analysis and manuscript preparation

Event	Weeks from primary completion date (PCD)
Primary completion date (PCD)	PCD
Laboratory Assays Completed	PCD + 7 months
Database clean-up complete	PCD + 8 months
Primary analysis report to Study Team. Primary analysis complete (PAC)	PCD + 9 months (PAC)
Draft manuscript submitted	PAC + 3 months
ClinicalTrials.gov results due	PCD + 1 year

## 9 Version History

Version	Changes Made	Effective Date
1.0		1/28/2019
